## Power and Sample Size (complete sample size justification available in Biostatistics Resource Core):

The current study is powered on the primary Aims 1 and 2. In the proposed study, response to a laboratory stressor, CREMA cue response and daily use data will be tested using GLMMs (assuming a Gaussian distribution) and the study will be powered to sufficiently address the least of the study treatment effect sizes determined to be clinically meaningful for the study hypothesis. Aim 1: Sinha and colleagues (Sinha, et al 2007), in a small pilot sample, demonstrated that lofexiding in combination with naltrexone attenuated craving and anger in response to laboratory drug and stress cues as compared to naltrexone alone. Results indicate a larger change in opioid craving scores in response to drug-related and stress cues occurs in placebo participants than lofexidine treated participants [Drug related cue response  $\Delta$ =2.2; SDP=2.6; between group Cohen's d=0.85, p<0.05 and stress cues response  $\Delta$ =2.1; SDP=2.4; between group Cohen's d=0.88, p<0.05]. Moreover, Fox and colleagues (2014) conducted a trial of quanfacine in cocaine-dependent individuals and noted stress and craving response to stress and drug-related imagery. They noted significant gender differences across treatment assignment for craving and stress response to drug-related imagery [Craving  $\Delta$ =3.0; SDP=3.8; Treatment x Sex Intx Cohen's d=0.79, p<0.05; Negative Emotion  $\Delta=3.0$ ; SDP=2.9; Treatment x Sex Intx Cohen's d=1.0, p<0.05]. Sample sizes in both the Sinha and Fox studies were somewhat small. Smaller but still clinically relevant effect sizes in an adequately powered study are anticipated. Therefore, a 20% reduction in craving and stress response from the previous studies is anticipated in the current design (Cohen's d=0.64 for the sex x treatment interaction on craving response). Aim 2: Kowalczyk and colleagues (2015), showed that daily life craving reports as measured by EMA were significantly reduced in opioid using participants randomized to clonidine as compared to placebo [6.3% (95% CI=5.6-7.1) vs. 11.8% (10.9-13.0); between group Cohen's *d*=1.6]. To assess the least of the differences anticipated in project 2, a sample size of 39 participants randomized to each female and males across active lofexidine and placebo groups would provide 80% power with a type 1 error rate of 5% to detect the treatment x sex interaction in craving and stress response to laboratory drug based cues (total n=156; 78 per group). We anticipate 25% attrition between randomization and the end of the 5-week active treatment period. Thus, inflating the necessary sample size to 68 participants randomized per treatment group with a total of n=136 randomized participants will provide adequate power.

**C.2.e.** Operational Plan and Research Timetable. Funding for five years is requested. The first three months will be spent hiring and training personnel and preparing for study initiation. We have established standard operating procedures, so we anticipate rapid study start-up. 54 months will be needed for participant recruitment and data collection. The final three months will be used for participant follow-up, data analysis and manuscript preparation.

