Statistics and Data Analysis (complete statistical/data analysis plan in Biostatistics Resource Core): Aim 1: Using a human laboratory paradigm, determine the impact of lofexidine on stress and drug cueinduced craving in women and men with OUDs: The primary study outcome of interest in Aim 1 is the differential craving, stress and anxiety response to a human laboratory paradigms containing both a stressor (TSST) and an opioid specific cue between participants randomized to lofexidine and placebo in addition to buprenorphine/methadone maintenance. Hypothesis 1: Lofexidine will attenuate drug craving and subjective stress response to a stress task in opioid-dependent individuals compared to individuals receiving placebo. Hypothesis 2: Lofexidine will attenuate drug craving and subjective stress response to a drug-related cue in opioid-dependent individuals. Hypothesis 3: The ameliorative effects of lofexidine on stress and cue-reactivity will be more pronounced in females than male subjects. To assess the hypothesis that lofexidine will attenuate drug craving and subjective stress response to the stressor and the opioid-related cue task, multilevel longitudinal GLMMs will be developed using all post-stressor and post-cue data. Initial models will control for study design aspects such as order (stressor or cue first), treatment assignment, and baseline craving and stress (task level). Covariate adjusted models will additionally include baseline characteristics determined to be correlated with study outcomes or those determined to be significant effect modifiers. To examine the differential effects of lofexidine on stress and cue-reactivity across female and male subjects, the models will have additional parameters added to include an indicator of participant gender and the interaction between gender and randomized treatment assignment. Relevant interactions will be assessed in all models. Least square means and associated standard errors will be assessed to compare craving and subjective stress response between treatment assignments at all time points.

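### The 39 per cell is the two-group sample size at d=0.64; read plainly, it gives about 51%, not 80%, power for the treatment-by-sex interaction, and the inputs that could recover 80% are not stated

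*Combined protocol and SAP*

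**What the plan says.** All of this is in section C.2.d of the combined protocol and SAP.

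- **Effect size.** Power and Sample Size takes a published interaction from a guanfacine trial, with a difference of 3.0 and a pooled SD of 3.8 ("Treatment x Sex Intx Cohen's d=0.79, p<0.05; Negative Emotion"). It then says that "a 20% reduction in craving and stress response from the previous studies is anticipated in the current design" and arrives at "Cohen's d=0.64 for the sex x treatment interaction on craving response".
- **Sample size.** It states that 39 in each sex-by-treatment cell, 156 in total and 78 per arm, "would provide 80% power with a type 1 error rate of 5% to detect the treatment x sex interaction in craving and stress response". The sentence limits this claim to the drug-cue task in the laboratory. The paragraph then allows for 25% attrition and gives 136 randomised, 68 per arm.
- **Analysis.** Aim 1 adds to the mixed model an indicator for gender and "the interaction between gender and randomized treatment assignment". This tests Hypothesis 3. Hypotheses 1 and 2 of the same aim concern the overall effect of lofexidine against placebo.
- **Not given.** The paragraph gives no formula, sidedness, number of ratings or correlation. It refers to a Biostatistics Resource Core for the full justification, which is not part of these documents.

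**The concern.** The total of 156 = 4 x 39 fixes 39 as a per-cell number. The same 39 is what the textbook two-group formula returns per group at 0.64. That formula would give 80% power for lofexidine against placebo within one sex. It would not give 80% for the difference between the sexes in that effect, which is the test the sentence names.

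The interaction is the effect on which the trial is sized. If the stated power is too high, a non-significant interaction would be reported as coming from a test with 80% power and read as evidence that the sexes respond alike. The plan as printed could not support that reading. The question is separate from the attrition arithmetic, because it arises even if all 156 are evaluable.

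**Working it through.** **Inputs from the plan:** d = 0.64; alpha 5% (two-sided assumed, as sidedness is not stated); power 80%; 39 per cell; 25% attrition; 136 randomised.

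**1. Reproduce the plan's figure.** Two-group formula, SD = 1:

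n per group = 2 x (1.96 + 0.84)^2 / 0.64^2 = 38.3, so 39.

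Power with 39 against 39 is 80.7% by the normal approximation and 79.7% by the noncentral t. The match is exact.

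**2. What d is.** The published benchmark is 3.0/3.8 = 0.79. The plan uses the same form, difference over SD_P, for its two-group effects in the lofexidine-naltrexone pilot (2.2/2.6 = 0.85 and 2.1/2.4 = 0.88). A 20% reduction of 0.79 gives 0.632, which the plan prints as 0.64. The natural reading is the difference of differences over the between-person SD.

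**3. Power for the interaction on that reading, single unadjusted outcome.** The contrast combines four independent cell means, so SE = SD x sqrt(4/n).

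- SE at 39 per cell = sqrt(4/39) = 0.320.
- Noncentrality = 0.64/0.320 = 2.00, so power is 51.5% (normal) or 51.0% (noncentral t, 152 df). One-sided, it is 64%.
- At the unreduced 0.79, power is 69%.
- Interaction detectable with 80% power = 2.80 x 0.320 = 0.90 SD.
- n per cell for 80% at 0.64 = 4 x (1.96 + 0.84)^2 / 0.64^2 = 76.6, so 77 (78 with the t distribution), about 310 in total.

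**4. Other readings of d.**

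- Contrast divided by sqrt(2) x SD: 0.64 x 1.414 = 0.905 person-SD, power 80.2%. This recovers the plan's figure.
- d taken as 2f (f = 0.32, N = 156): power 97.8%.

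**5. Gains from the specified model.** The Aim 1 model uses all post-task data and adjusts for the task-level baseline. The design-timing text of Phase Two gives four post-task measurements: at the end of the task and 5, 30 and 60 minutes later. If the effect is constant over the four ratings and 0.64 is on the single-rating scale, the variance is multiplied by V, and SE = sqrt(4V/n). Let rho be the correlation among post-task ratings and r the correlation of one rating with baseline. Then V = (1 + 3 rho)/4 - r^2. If the baseline correlation is instead defined with the four-rating mean, V = [(1 + 3 rho)/4] x (1 - r^2). All correlations below are assumptions.

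| Assumption | V | Power at 39 per cell |
|---|---|---|
| rho 0.9, r 0 | 0.925 | 54% |
| rho 0.5, r 0.5 with the mean | 0.469 | 83% |
| rho 0.5, r 0.5 with one rating | 0.375 | 90% |
| one common correlation, least favourable value (0.375) | 0.391 | 89% |

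With baseline adjustment of a single rating alone, 80% needs V of about 0.51, a baseline correlation of about 0.70.

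**6. The evaluable number the trial expects.** 136 x 0.75 = 102, or 25.5 per cell if the cells are balanced. SE = sqrt(4/25.5) = 0.396; noncentrality = 0.64/0.396 = 1.62; unadjusted power is about 36%. With all 136 evaluable (34 per cell) it is about 46%.

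**The case against.** The strongest reply has three parts.

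**The definition of d.** A reader might infer that no interpretation of d produces 80%. That is not so. The plan never defines SD_P or says what its difference subtracts for the interaction, and standardising by the SD of a difference gives 80.2%. The person-SD reading is the more natural one, because the plan uses the same symbol and ratio for its two-group effects, but it is an inference.

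**The analysis model.** A reader might also infer that the trial's interaction power simply is 51%, close to a coin toss. The documents do not support that either. The 51% belongs to one unadjusted rating, while the plan specifies four post-task ratings with baseline adjustment, and the power paragraph says it refers to mixed models. With one common correlation among all five ratings, power at 39 per cell would be at least 89%. That figure rests on a constant effect over time and on 0.64 being a single-rating effect; if SD_P is already the SD of a change score, the gain is smaller. This objection stands as a limit on the 51%. It does not support the printed 80%, because the plan states no correlation and 39 matches the unadjusted two-group formula exactly.

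**The place of the interaction.** It would go too far to treat the interaction as the trial's only primary question. Sections A.6 and A.7 do give the exploration of gender differences as the primary objective. But Aim 1 Hypotheses 1 and 2 are main effects, the sex hypothesis in Aim 2 is labelled exploratory, and the monitoring plan names stress reactivity as the primary outcome. At 78 per arm, a main effect of 0.64 has 98% power.

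The fuller justification in the Biostatistics Resource Core may contain the missing inputs. It could not be checked, and the protocol sentence still has to agree with it.

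**Conclusion.** The concern holds in this form: 39 per cell is the two-group size at d=0.64, and the plan presents it as giving 80% power for an interaction. On the plan's own construction of d, with a single unadjusted outcome and all 156 evaluable, the power is about 51% and the detectable interaction about 0.90 SD, which is larger than even the unreduced 0.79 benchmark.

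The 80% can be recovered by a different standardisation of d or by sufficient gains from repeated ratings and baseline adjustment, but the plan states neither. Those gains put power at 39 per cell anywhere from about 54% to 90% or more. The figures assume a two-sided 5% test, equal cells and a common SD; section C.2.c.5 lists other substance use and childhood trauma, not sex, as stratification factors, so equal cells are not guaranteed.

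The conclusion concerns the interaction in Aim 1 Hypothesis 3, the effect on which the trial is sized. It does not show that the main-effect hypotheses are underpowered. The printed figure should be corrected or its basis supplied.

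**What to change.** Rewrite the Power and Sample Size paragraph of C.2.d so that it:

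1. Defines the difference, SD_P and d for the interaction, including whether SD_P refers to a single rating, a change score or a difference.
2. States that 39 evaluable per cell gives 80% power for lofexidine against placebo within one sex at d=0.64, and about 51% for an interaction of 0.64 SD on a single unadjusted outcome (detectable interaction about 0.90 SD).
3. If the baseline-adjusted repeated-measures model is relied on, gives the number of ratings, the assumed correlations and the resulting power.
4. Reports interaction power at the evaluable number expected from 136 randomised with 25% attrition: about 25.5 per cell, about 36% unadjusted, plus the model-based figure if one is claimed.
5. Describes the interaction as the effect the trial is sized on (Aim 1 Hypothesis 3) and notes that Hypotheses 1 and 2 are main effects.

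The Biostatistics Resource Core text should be brought into line. The cost is a reworded paragraph and, unless the missing inputs support it, a less favourable power figure. No extra enrolment and no change to the design or analysis is needed.

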- g. Virtual monitoring: In order to reduce face-to-face visits when necessary, remote monitoring may be done during the medication phase. At the randomization visit, patients will be given a wrist blood pressure cuff for at home monitoring, and they will be trained in testing orthostatic blood pressure. Patients will come to the clinic once a week for a UDS, to meet with staff/medical personnel and have ave orthostatic testing done, and receive medication refills. Two weekly visits will be conducted via Telehealth. Patients will be observed doing a saliva drug screen and doing orthostatic blood pressure testing. If patients are symptomatic or having difficulty with telehealth procedures, they may be asked to attend the clinic more frequently. Participants who are not comfortable with telehealth procedures may choose to attend clinic visits instead.
- C.2.c.5. Phase Two: Scripted Opioid Imagery and Laboratory Induction Session (Days 39 and 40). At the end of the five-week period of lofexidine or placebo administration, participants will return to complete a scripted opioid imagery taksk and a laboratory stress task (Trier Social Stress TSST). Tasks will Test, counterbalanced. Subjects will remain on study medications for the test days. Subjects who miss their scheduled visits may be re-scheduled for up to one week. a. Session Preparation. Participants will be instructed to arrive at 8:00am on the test days, and to avoid caffeinated beverages since caffeine can introduce variability in heart rate response. If the individual is nicotine-dependent, (s)he will be provided with a nicotine patch throughout their study visit. Upon arrival, the participant will be breathalyzed and

|            | TAB             | BLE 3: LAB TESTING TIMELINE                                |  |  |
|------------|-----------------|--|--|--|
|            | 8:15am          | UDS, Saliva  |  |  |
|            | 8:35 am         | Relaxation   |  |  |
| Test Day 1 | 8:55am          | Baseline 1 Subjective, physiologic, endocrine measurement  |  |  |
| st [       | 9:00am - 9:15am | TSST/Imagery   |  |  |
| Te         | 9:15am          | Subjective, physiologic, endocrine measurement             |  |  |
|            | 9:20am          | Subjective, physiologic, endocrine measurement             |  |  |
|            | 9:45am          | Subjective, physiologic, endocrine measurement             |  |  |

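### The attrition step in the sample-size section lowers the requirement from 156 to 136; the figures must be reconciled and Aim 1 interaction power restated for about 102 expected evaluable participants

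*Combined protocol and SAP*

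**What the plan says.** All the sizing is in the Power and Sample Size part of section C.2.d.

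- Effect: a published interaction ("Treatment x Sex Intx Cohen's d=0.79") is reduced by 20% to "Cohen's d=0.64 for the sex x treatment interaction on craving response".
- Requirement: "a sample size of 39 participants randomized to each female and males across active lofexidine and placebo groups would provide 80% power", with a 5% type 1 error rate, written out as "total n=156; 78 per group".
- Attrition: "We anticipate 25% attrition between randomization and the end of the 5-week active treatment period".
- Conclusion: "Thus, inflating the necessary sample size to 68 participants randomized per treatment group with a total of n=136 randomized participants will provide adequate power".

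The section heading refers elsewhere for detail: "complete sample size justification available in Biostatistics Resource Core". That document is not part of the protocol and SAP.

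Five other places bear on the point.

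- C.2.a (Participants) and Protection of Human Subjects repeat 136, as 68 men and 68 women, and speak of recruiting them.
- C.2.b (Recruitment) requires four participants per month. C.2.a and C.2.e give 54 months for recruitment.
- The Aim 1 sessions come late. In C.2.c.5, Phase Two: "At the end of the five-week period of lofexidine or placebo administration, participants will return to complete a scripted opioid imagery" task and the TSST.
- C.2.c.5, Phase 1, item d stratifies randomisation on other substance use and childhood trauma. Sex is not listed.
- The Aim 1 analysis is a mixed model of all post-task measurements, adjusted for baseline, with a gender-by-treatment term for Hypothesis 3.

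**The concern.** An allowance for attrition raises a sample size. Here the number after the allowance is 20 below the number before it, so the sentence that calls 136 adequate does not follow from the two sentences before it.

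This matters because the study is sized on the interaction, and sections A.6 and A.7 give the exploration of gender differences as the primary objective. If the 156 is right, 136 randomised leaves the interaction test well short of the claimed 80%. If the 156 is wrong, the plan states no basis for the power of the trial being run. In either case the stated power cannot be used when a non-significant interaction is interpreted.

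**Working it through.** **Inputs (Power and Sample Size):** d = 0.64; 5% type 1 error, taken as two-sided because the plan does not say; 80% power; 39 per cell, 78 per group, 156 total; 25% attrition; 136 randomised, 68 per group.

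**1. Reproducing the requirement.** The formula for two independent means, n = 2 × ((1.960 + 0.842)/0.64)², gives 38.3, so 39. Then 4 × 39 = 156 and 2 × 39 = 78. The figures before attrition agree with each other and match a simple two-group formula applied within each sex. (0.79 × 0.8 is 0.632 rather than 0.64; that changes 39 only to 40.)

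**2. The attrition step.** Number to randomise = requirement / (1 − 0.25).

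| Requirement taken | Result |
|---|---|
| 156 total | 156/0.75 = 208 |
| 78 total (39 per treatment group) | 78/0.75 = 104 |
| 102 total (51 per group), not stated anywhere | 102/0.75 = 136 |

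The shortcut 156 × 1.25 gives 195. No stated requirement leads to 136.

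**3. Expected evaluable for Aim 1.** The laboratory sessions come at the end of treatment, so the full 25% applies: 136 × 0.75 = 102, or 51 per arm. With sex balanced across arms this is 102/4 = 25.5 per cell. Compared with 156, that is 1 − 102/156 = 35% fewer.

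**4. Interaction power if 39 per cell does give 80%.** Two-group t-test, d = 0.64, two-sided 5%:

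| n per cell | Total | Power |
|---|---|---|
| 39 | 156 | 79.7% |
| 34 | 136, no attrition | 73.9% |
| 25.5 | 102 | 61.0% |

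The effect detectable with 80% power at 25.5 per cell is d = 0.80. As a cross-check, take a four-cell contrast with SE = 2 × SD × √(v/n), n per cell and 4n − 4 degrees of freedom. Setting v so that 39 per cell gives exactly 80% (v = 0.502) gives 61.7% at 25.5 and a detectable effect of 0.79.

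**5. Interaction power if the meaning of d is left open.** The same SE is used. The documents give no value of v or of any correlation, so these rows are assumptions. For baseline-adjusted means of four post-task measures, v = (1 + 3 × post–post correlation)/4 − (baseline–post correlation)².

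| Reading of d = 0.64 | v | At 25.5 per cell | At 39 per cell |
|---|---|---|---|
| Difference of differences, unadjusted | 1 | 36% | 51% |
| Adjusted; post–post 0.8, baseline–post 0.4 | 0.69 | 49% | 67% |
| Adjusted; both 0.5 | 0.375 | 74% | 90% |
| Adjusted; both 0.7 | 0.285 | 85% | 96% |
| Half-contrast (difference of differences = 1.28 SD) | 1 | 89% | 98% |

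None of these five rows gives 80% at 39 per cell.

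**6. Treatment main effect.** d = 0.64 with 51 per arm: 89%.

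**7. Recruitment rate.** 4 per month × 54 months = 216. By comparison, 136/54 = 2.5 per month and 208/54 = 3.9 per month.

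**The case against.** Three arguments can be made for the plan.

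*The full justification lies in another document and may support 136.* It may. That does not make the printed sentence correct, because 136 is presented as an inflation of the 156 stated just before it. The argument does stop a reader from concluding which figure is wrong.

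*A loss of power is not established.* This stands. The 61–62% depends on the 80% at 156, which may itself be the error, and the readings in step 5 run from inadequate to adequate at 102. A reader might go further in the plan's favour and infer that baseline-adjusted repeated measures guarantee about 73% or more. That floor holds only if the baseline–post correlation equals the post–post correlations. Post-task measures fall at 0, 5, 30 and 60 minutes and the baseline precedes the task, so equality is doubtful, and the 49% row breaks the floor.

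*The main questions are adequately powered.* Aim 1 Hypotheses 1 and 2 are treatment effects with about 89% power at d = 0.64, the Aim 2 gender hypothesis is labelled exploratory, and section A.6 speaks of exploring gender differences. This narrows the point to Aim 1 Hypothesis 3. It does not remove it, because the section bases its 80% on that interaction. A confidence interval for the interaction would also inform a reader whatever the planned power.

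The figure of 102 needs care too. It is an expectation for the laboratory endpoint only; Aim 2 uses data collected throughout treatment, to which dropouts may contribute. Sex is not a stratification factor, so 25–26 per cell is not guaranteed. C.2.a speaks of recruiting 136 and the power section of randomising 136, and C.2.c.5 places two negative urine screens before randomisation, so fewer could be randomised if 136 counts recruits.

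**Conclusion.** The concern holds. The step from 156 to 136 is wrong as written: 25% attrition on 156 gives 208, and 136 corresponds to an unstated requirement of 102. This rests only on figures in the section.

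The size of the consequence is conditional. If 156 does give 80%, Aim 1 interaction power at the expected 102 evaluable is about 61–62% (about 74% with no attrition), and the effect detectable with 80% power returns to about 0.80, close to the undiscounted 0.79. If it does not, the illustrations at 102 are about 36% for an unadjusted difference of differences, roughly 49–85% for baseline-adjusted repeated measures with no guaranteed floor, and about 89% for a half-contrast.

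A reader might infer that the trial should randomise 208, or that it is shown to be underpowered. The documents support neither, because they do not settle whether 39/156 or 136 is in error. The recruitment arithmetic (216 over 54 months) lies nearer 208 than 136, but it may include people never randomised. It belongs in the reconciliation and does not decide it.

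**What to change.** Revise the Power and Sample Size section as follows.

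1. Reconcile 39 per cell, 156 and 136, and say which requirement was divided by 0.75. Account for the C.2.b rate of four per month over 54 months.
2. Correct or delete the sentence that presents 136 as an inflated figure with adequate power.
3. For the reconciled number randomised (136 if it stands), state the expected evaluable number for the Aim 1 laboratory endpoint (about 102 for 136), and say whether 136 counts people recruited or randomised.
4. Restate Aim 1 interaction power and the detectable difference at that number. Define the contrast (difference of differences or other), the SD that scales it, and the correlations assumed for the baseline-adjusted repeated measures.
5. If that power is below 80%, say so.

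The cost is rewording and a short recalculation. These changes add no patients and alter no hypothesis or planned model. The downside is that the stated interaction power may be less favourable than 80%.
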